1.5.1.1. Infusion Reactions

Elotuzumab can cause infusion reactions. Infusion reactions were reported in approximately 10% of subjects treated with elotuzumab with lenalidomide and dexamethasone in the randomized trial in multiple myeloma. All reports of infusion reaction were Grade 3 or lower. Grade 3 infusion reactions occurred in 1% of subjects. The most common symptoms of an infusion reaction included fever, chills, and hypertension. Bradycardia and hypotension also developed during infusions.

In the trial, 5% of subjects required interruption of the administration of elotuzumab for a median of 25 minutes due to infusion reactions, and 1% of subjects discontinued due to infusion reactions. Of the subjects who experienced an infusion reaction, 70% (23/33) had them during the first dose.

Administer premedication consisting of dexamethasone, antihistamines (H1 and H2 blockers) and acetaminophen prior to elotuzumab infusion (See section 6.5.2)

Interrupt elotuzumab infusion for Grade 2 or higher infusion reactions and institute appropriate medical management (See section 6.5.2).

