6.6. Dose-Modification Guidelines

The following sections and tables summarize dosing modifications of elotuzumab, carfilzomib, lenalidomide, and dexamethasone to manage possible toxicity. Dose modifications different from those stated in the protocol should be discussed with the Lead Principal Investigator. Administration of carfilzomib and lenalidomide will be discontinued in the event of any other toxicity that, in the opinion of the Lead, Secondary Site, or Treating Investigator, warrants discontinuation.

In addition to dose reductions, administration of elotuzumab, carfilzomib and lenalidomide will be held temporarily in the event of a treatment-related toxicity at the Treating Investigator's discretion. Study treatment may be reintroduced if resolution of the event to the baseline value or to \leq Grade 1 within 21 days; otherwise study drug will be permanently discontinued. Any deviations from this plan must be approved by the Lead Principal Investigator.

If a subject's elotuzumab administration is delayed on day 1 of a cycle, carfilzomib, lenalidomide, and dexamethasone will also be delayed until the elotuzumab is resumed, which would then become the new day 1 of that cycle.

If a subject's elotuzumab is held in the middle of a cycle, carfilzomib, dexamethasone, and lenalidomide dosing will continue as scheduled. If the subject's elotuzumab is delayed during the cycle and is resumed within the designated window, (+/-3 days Cycles 1 and 2; +/-7 days Cycles 3 and beyond) the subject may receive the scheduled dose. If the elotuzumab is not resumed within the given window (+/-3 days Cycles 1 and 2; +/-7 days Cycles 3 and beyond), the subject is to omit that dose, and resume dosing at the next dosing time point.

If a study drug (except dexamethasone) is discontinued, the subject may continue on trial. However, if the discontinuation happens prior to the end of cycle 8 (1^{ary} endpoint), the subjects will Page 45

continue to be treated and will only be included on the intent to treat analysis.

All clinically-significant non-hematologic toxicities must be resolved to Grade 1 or baseline.

Dose reduction levels of elotuzumab, carfilzomib, lenalidomide, and dexamethasone for toxicity management of individual subjects are provided below:

Table 6-1 Carfilzomib Dose Adjustments

Nominal carfilzomib dose	Dose -1	Dose -2	Dose -3	Dose -4
70 mg/m^2	56 mg/m^2	45 mg/m^2	36 mg/m^2	27 mg/m^2

Table 6-1 Lenalidomide Dose Adjustments

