6.6.2. Guidelines for Elotuzumab Infusion and pre-medication in Subjects with Infusion Reactions

Required Treatments

Dexamethasone

On weeks without elotuzumab administer the weekly dose of 40 mg (Cycles 3-4) or 20mg (Cycles 5+) dexamethasone orally on Day 1, 8, 15, and 22 (-1 to +3 days). At the investigator's discretion, the oral dexamethasone may be given as a split dose over 2 consecutive days each week.

At the discretion of the investigator, the oral dexamethasone component may be given as a split dose 12-24 hours and 3 hours prior to elotuzumab.

Premedication Before Elotuzumab:

1. Dexamethasone 20 mg IV (C1 and 2), 40mg PO (C3-4), or 20mg (C5+) not longer than 3 hours prior to the start of elotuzumab infusion when they coincide, and 20mg PO the day after elotuzumab infusion (C1-2 only).

AND

- 2. H1 blocker: diphenhydramine (25 50 mg PO or IV) or equivalent (45-90 minutes prior to the start of infusion)
- 3. H2 blocker: ranitidine (50 mg IV) or equivalent (45-90 mins prior to the start of infusion)
- 4. Acetaminophen (650 1000 mg PO), (45-90 mins prior to the start of infusion

Premedication Regimen in Subjects With a Prior Infusion Reaction

Subjects with prior infusion reaction must receive H1, H2 blockers and acetaminophen at maximum doses specified above.

Table 6-9 Elotuzumab infusion in subjects with infusion reactions

Prior Infusion Reaction	Corticosteroid premedication prior to elotuzumab
None or Only Grade 1 infusion reaction	no change
Prior Grade 2 infusion reaction	Split dexamethasone dose on days of elotuzumab; e.g. for dose level 40 mg to 28 mg prior to carfilzomib and 12 mg prior to elotuzumab
Prior Grade 3 or recurrent Grade 2 infusion reaction	8 mg oral dexamethasone (12 - 24 hrs prior to elotuzumab) AND 8 mg oral dexamethasone (at least 3 hrs prior to elotuzumab) AND 24 mg IV dexamethasone at least 45-90 min prior to elotuzumab

At the discretion of the investigator, the 40 mg oral dexamethasone component may be given as a split dose: 20 mg PO (12–24 hours prior to elotuzumab) AND 20 mg PO (3 hours prior to elotuzumab).

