If a subject with a prior Grade 2-3 infusion reaction also requires dose reduction of dexamethasone, the weekly dexamethasone on the days of elotuzumab infusion should be no lower than 8 mg IV (on the day of elotuzumab infusion at least 45 minutes prior to elotuzumab). Subjects with a Grade 4 elotuzumab infusion reaction must have elotuzumab permanently discontinued. Additionally, subjects who have a recurrence of \geq Grade 2 infusion reactions with subsequent doses and subjects who have a true hypersensitivity reaction at \geq Grade 2 should have elotuzumab permanently discontinued (but may continue on KRd).

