6.6.2.1. Elotuzumab Dose Delay or Interruption

If toxicity is considered to be related to elotuzumab, elotuzumab should delayed, interrupted, or discontinued (please refer to tables 6-5 and 6-6 for further guidelines). However, if dexamethasone is delayed or discontinued, the administration of elotuzumab should be based on clinical judgment (ie, risk of hypersensitivity).

If a \geq Grade 2 infusion reaction occurs during elotuzumab administration, the infusion must be interrupted. Upon resolution to \leq Grade 1, elotuzumab should be restarted at 0.5 mL/min and may be gradually increased at a rate of 0.5 mL/min every 30 minutes as tolerated to the rate at which the infusion reaction occurred. If there is no recurrence of the infusion reaction, the escalation regimen can be resumed (Table 6-9).

Subjects who experience an infusion reaction require vital signs to be monitored every 30 minutes for 2 hours after the end of the elotuzumab infusion. If the infusion reaction recurs, the elotuzumab infusion must be stopped and not restarted on that day. Very severe infusion reactions may require permanent discontinuation of elotuzumab therapy and emergency treatment.

If a subject's elotuzumab administration is delayed on day 1 of a cycle, carfilzomib, lenalidomide, and dexamethasone will also be delayed until the elotuzumab is resumed, which would then become the new day 1 of that cycle.

If a subject's elotuzumab is held in the middle of a cycle, carfilzomib, dexamethasone, and lenalidomide dosing will continue as scheduled. If the subject's elotuzumab is delayed during the cycle and is resumed within the designated window, (+/-3 days Cycles 1 and 2; +/-7 days Cycles 3 and beyond) the subject may receive the scheduled dose. If the elotuzumab is not resumed within the given window (+/-3 days Cycles 1 and 2; +/-7 days Cycles 3 and beyond), the subject is to omit that dose, and resume dosing at the next dosing time point.

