Once the elotuzumab infusion-related reaction has resolved to Grade ≤ 1 , the infusion can be restarted at 0.5 mL/minute. If symptoms do not recur after 30 minutes, the infusion rate may be increased in a stepwise fashion (0.5 mL/minute every 30 minutes) to the rate at which the infusion reaction occurred. If no recurrence of the infusion reaction, the escalation regimen can be resumed. Subjects who experience an infusion reaction require vital signs to be monitored every 30 minutes for 1 or 2 hours after the end of the elotuzumab infusion (as clinically indicated). If the elotuzumab infusion reaction recurs, the infusion must be stopped and not restarted on that day. Appropriate therapy should be administered to address the subject's signs and symptoms. The infusion can be reattempted at the next protocol defined infusion time point at the investigator's discretion with additional premedication.

Infusion reactions after the completion of elotuzumab infusion: Should a Grade 2 or 3 infusion reaction occur following the completion of an elotuzumab infusion, the subject should be treated as clinically indicated with 1 or more of the following medications or interventions: diphenhydramine, acetaminophen, hydrocortisone, H2 inhibitor, leukotriene inhibitor, oxygen inhalation, epinephrine, bronchodialators, or other supportive measures as indicated.

Elotuzumab infusions on subsequent weeks after a prior Grade 2 or 3 infusion reaction: Subjects with a prior Grade 2 or 3 infusion reactions should have the next infusion started at 0.5 mL/min and then escalated in a stepwise fashion (0.5 mL/minute every 30 minutes) to the rate at which the infusion reaction occurred. If no Grade ≥2 infusion reaction occurs, the escalation regimen may be resumed, and the next infusion may be initiated as planned per regimen.

Grade 4 Infusion Reaction: Subjects with a Grade 4 elotuzumab infusion reaction must have elotuzumab permanently discontinued.

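### Section 6.6.2 gives opposite instructions for Grade 2 elotuzumab infusion reactions at two separate doses: stepped-up premedication in Table 6-9, permanent discontinuation in the text below it

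*Combined protocol and SAP*

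**What the plan says.** Table 6-9 sets the corticosteroid to be given before elotuzumab according to the subject's reaction history. Its second row covers a prior Grade 2 reaction. Its third row is labelled "Prior Grade 3 or recurrent Grade 2 infusion reaction" and prescribes two oral dexamethasone doses of 8 mg and one intravenous dose of 24 mg, all before the next elotuzumab.

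The paragraph after the table first requires a permanent stop for Grade 4. It then adds two further groups: subjects with a recurrence, at Grade 2 or higher, of "infusion reactions with subsequent doses and subjects who have a true hypersensitivity reaction" at Grade 2 or higher. Both groups "should have elotuzumab permanently discontinued (but may continue on KRd").

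Two other sections bear on this:

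- Section 6.6.2.1, on a restarted infusion: "If the infusion reaction recurs, the elotuzumab infusion must be stopped and not restarted on that day".
- Section 6.10.1 gives the same same-day stop and says the infusion "can be reattempted at the next protocol defined infusion time point", at the investigator's discretion and with added premedication. For later weeks it says: "Subjects with a prior Grade 2 or 3 infusion reactions should have the next infusion started at 0.5 mL/min". The only permanent stop it names is for Grade 4.

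**The concern.** The third row assumes that elotuzumab will be given again, while the paragraph below says it should not be. If *recurrent Grade 2* includes a second Grade 2 reaction at a later dose, one subject falls under both. Section 6.6.2 neither defines the word nor says which instruction ranks first.

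At stake is a rule on re-exposure. A site working from Table 6-9, or from section 6.10.1 alone, could infuse again a subject whom the text says should stop. Section 6.6 offers a check: "Dose modifications different from those stated in the protocol should be discussed with the Lead Principal Investigator". But a site that believes it is following the third row sees no departure from the protocol and has no reason to call.

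**Working it through.** The plan gives no figure here, so the main check is a comparison of wording. Take the four ways a subject can have a Grade 2 or 3 reaction at one dose and another at a later dose, leaving out true hypersensitivity, which has its own stop.

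| Earlier dose, later dose | Fits the third-row label? | Fits the stop in the text? | Best reading |
|---|---|---|---|
| Grade 2, Grade 2 | Yes if *recurrent* covers later doses; no if it means one infusion | Yes | Opposite instructions unless the one-infusion meaning is adopted |
| Grade 2, Grade 3 | Yes (prior Grade 3) | Yes | Stop governs |
| Grade 3, Grade 2 | Yes (prior Grade 3) | Yes | Stop governs |
| Grade 3, Grade 3 | Yes (prior Grade 3) | Yes | Stop governs |

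The first line differs from the others. After a first Grade 3 reaction the stop has not been triggered, so the Grade 3 half of the third row has subjects to apply to. A later reaction then triggers the stop, and the two instructions work in order. If *recurrent Grade 2* means a second reaction at a later dose, that half of the row describes exactly the subjects told to stop, and it has nobody left to premedicate. Either the word means recurrence within one infusion, or the table allows a rechallenge that the text advises against. Section 6.6.2 does not say which.

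**Size.** Inputs are the rates in section 1.5.1.1, from the randomized trial of elotuzumab with lenalidomide and dexamethasone, applied to the planned 55 subjects:

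- Any infusion reaction: 0.10 × 55 = 5.5.
- Infusion interrupted ("5% of subjects required interruption of the administration of elotuzumab"): 0.05 × 55 = 2.75.
- Grade 3: 0.01 × 55 = 0.55.
- Stopped elotuzumab for infusion reactions: 0.01 × 55 = 0.55.

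Assume interruption marks Grade 2 or higher, since sections 1.5.1.1 and 6.6.2.1 call for interruption from that grade. Let r be the share of those subjects who react again at a later dose:

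- Subjects with recurrence at a later dose = 2.75 × r. With r from 0 to 1, this is 0 to 2.75.
- Starting from Grade 2 only, and assuming every Grade 3 reaction was interrupted: (2.75 − 0.55) × r = 2.2 × r, or 0 to 2.2.

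The documents give no value for r. Among subjects who reacted, 23/33 = 69.7% did so during the first dose. That points to the low end but is not a recurrence rate.

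**The case against.** The strongest reply is that the section can be read without conflict. The table says how to premedicate if elotuzumab is given, and the text just below says who should stop. A stop ordinarily ends the need for premedication. Nobody sees a conflict when a Grade 3 reaction is followed by a Grade 4 one, though no sentence ranks the table and the text there either. Sections 6.6.2.1 and 6.10.1 speak of recurrence within one infusion, and the re-attempt with added premedication in 6.10.1 fits the third row well. The text below the table, by contrast, is expressly about later doses. Taken together, these readings leave none of the four sequences in conflict.

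Most of this stands. A reader might infer that all four sequences receive contradictory instructions, because each can be matched to both the third-row label and the stop. The documents do not support that for the three sequences with a Grade 3 reaction, for the reason given under the table above.

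For Grade 2 followed by Grade 2, the reply depends on a meaning of *recurrent* imported from other sections. The row order invites the opposite meaning: *prior Grade 2* followed by *recurrent Grade 2* looks like escalation after a second reaction at a later dose.

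Three smaller points also have some force:

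- The text says *should* for recurrence and *must* for Grade 4. This may leave room for judgement, but if a rechallenge is meant to be possible, the text ought to say so.
- The starting rate in section 6.10.1 is not a competing rule. It sets the speed of the next infusion and is silent on a second reaction at a later dose.
- Section 6.4.1 refers to separate administration guidelines, which are not among the documents and may settle the point. The bi-weekly safety review in section 13.7 may catch errors after they occur.

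**Conclusion.** The point holds in a limited form. One sequence, Grade 2 reactions at two separate doses, meets opposite instructions within section 6.6.2 unless *recurrent* is given a meaning the section does not state. Section 6.10.1 adds to the difficulty by leaving out the recurrence stop, so a site reading only that section would not find it.

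The likely number affected is 0 to about 3 of 55 subjects. This assumes that rates from the earlier trial carry over, that interruption marks Grade 2 or higher, and that the recurrence rate could lie anywhere from 0 to 100%. Reactions that begin after an infusion ends would not be counted as interruptions. The 5.5 expected subjects with any reaction are a looser outer bound, but they include Grade 1.

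Alpha, power and sample size are unaffected. This is a minor internal inconsistency in a safety rule, not a fault in the design, and it merits correction because the rule concerns re-exposure and the correction is short.

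**What to change.** 1. Change the third-row label of Table 6-9 to: *first Grade 3 reaction, or Grade 2 reaction recurring within the same infusion*.
2. Add under the table: *any Grade 2 or higher reaction that recurs at a later dose is governed by the permanent discontinuation in the text below, whichever row applied earlier*.
3. Repeat that sentence in section 6.10.1, under infusions in later weeks.

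The second change does the essential work. A subject with Grade 2 and then a first Grade 3 reaction would still fit the reworded row, and so, at the time of the first reaction, would one whose Grade 3 reaction came first. With the added sentence, all four two-dose sequences lead to stopping. A first Grade 3 reaction with no earlier reaction of Grade 2 or higher, or a Grade 2 recurrence confined to one infusion, leads to the third-row premedication.

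The cost is one table label and two sentences, with no change to design or sample size. The downside is that a few subjects may stop elotuzumab who could have been rechallenged. If the sponsor wants to keep that option, the text below the table should instead say how many recurrences under stepped-up premedication trigger the stop.

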6.6.2.1. Elotuzumab Dose Delay or Interruption

If toxicity is considered to be related to elotuzumab, elotuzumab should delayed, interrupted, or discontinued (please refer to tables 6-5 and 6-6 for further guidelines). However, if dexamethasone is delayed or discontinued, the administration of elotuzumab should be based on clinical judgment (ie, risk of hypersensitivity).

If a \geq Grade 2 infusion reaction occurs during elotuzumab administration, the infusion must be interrupted. Upon resolution to \leq Grade 1, elotuzumab should be restarted at 0.5 mL/min and may be gradually increased at a rate of 0.5 mL/min every 30 minutes as tolerated to the rate at which the infusion reaction occurred. If there is no recurrence of the infusion reaction, the escalation regimen can be resumed (Table 6-9).

Subjects who experience an infusion reaction require vital signs to be monitored every 30 minutes for 2 hours after the end of the elotuzumab infusion. If the infusion reaction recurs, the elotuzumab infusion must be stopped and not restarted on that day. Very severe infusion reactions may require permanent discontinuation of elotuzumab therapy and emergency treatment.

If a subject's elotuzumab administration is delayed on day 1 of a cycle, carfilzomib, lenalidomide, and dexamethasone will also be delayed until the elotuzumab is resumed, which would then become the new day 1 of that cycle.

If a subject's elotuzumab is held in the middle of a cycle, carfilzomib, dexamethasone, and lenalidomide dosing will continue as scheduled. If the subject's elotuzumab is delayed during the cycle and is resumed within the designated window, (+/-3 days Cycles 1 and 2; +/-7 days Cycles 3 and beyond) the subject may receive the scheduled dose. If the elotuzumab is not resumed within the given window (+/-3 days Cycles 1 and 2; +/-7 days Cycles 3 and beyond), the subject is to omit that dose, and resume dosing at the next dosing time point.

6.7. Response Evaluation

The first response assessment should be completed at Cycle 1 Day 15. If at any time throughout the treatment a complete response or better is suspected, a complete disease assessment should be performed to confirm response according to IMWG criteria:

Myeloma Disease Assessment – M-protein determination: laboratory

• Serum Protein

- Serum Protein Electrophoresis (SPEP) and immunofixation
- Urine Protein Electrophoresis (UPEP) and immunofixation
- 24hr Urine

- Serum Free Light Chains
- Serum quantitative immunoglobulins (Igs)

A serum sample from blood at landmark timepoints (after C4, 8, 12, and 18, 24 months after C1D1, and yearly after) will be required for banking at the University of Chicago for later M-spike analysis with a new elotuzumab interference assay. The analysis of banked samples by elotuzumab interference assay will be performed using Mass Spectrometry by BMS.

Bone Marrow Biopsy

Quantify percent myeloma cell involvement, and obtain bone marrow aspirate for conventional cytogenetics and fluorescent *in situ* hybridization. For subjects who give consent for correlative samples, an additional aspirate sample should be collected at screening, at time of complete response (if applicable), at the end of cycles 8 and 12, EOT, and time of progression.

Radiographic Imaging

As per standard of care

Progressive disease requires 2 consecutive assessments made at any time before classification of relapse or progression and/or institution of new therapy when clinically possible.

6.8. Study Termination

Any Grade 5 toxicity related to study treatment will prompt stopping of the trial until further review is completed. Additionally, development of Grade 4 of non-hematologic toxicities in 2 or more patients will prompt the DSMB to stop the study for review to determine whether the trial should be terminated due to excessive toxicity.

6.9. Treatment Discontinuation

Subjects will be free to discontinue treatment or withdraw from the study at any time, for any reason, or they may be withdrawn/ removed if necessary in order to protect their health (see reasons for withdrawal below).

Subjects will be removed from further treatment for the following reasons:

- Disease Progression
- Non-compliance with study procedures
- Subject no longer consents to participate in the study
- Intercurrent illness that interferes with study assessments
- Treatment-related toxicity requiring treatment discontinuation
- Incidence or severity of AEs that indicates a potential health hazard to the subject
- For the fourth occurrence of the same Grade ≥ 3 non-hematological toxicity
- A delay in treatment > 21 days unless approved by the Lead Principal Investigator as well that due to Congestive Heart Failure unresolved for > 28 days the treatment shall be discontinued (see table 6-7)
- Treating Investigator discretion
- Requirement for alternative therapy
- Suspected or positive pregnancy

• Termination of the study by the sponsor

The Lead Principal Investigator should be contacted regarding any impending discontinuation of a study subject. If the reason for withdrawal is the occurrence of an AE, the subject will be followed until such events resolve, stabilize, and, according to the Treating Investigator's judgment, there is no need for further follow-up. The reason for withdrawal from study must be documented in the case report form.

In case of premature discontinuation of the study treatment, the investigations scheduled for the EOT should be performed, if possible. Should a subject decide to withdraw, every effort will be made to complete and report the observations as thoroughly as possible. The Treating Investigator should contact the subject to determine as completely as possible the reason for the withdrawal. A complete final evaluation at the time of the subject's withdrawal should be made, with an explanation of why the subject is withdrawing from the study.

